3.1 General Design

TMS will be administered to either the fMRI-guided target or DLPFC in a randomized, single-blind design. 40 patients diagnosed with Post-Traumatic Stress Disorder (PTSD) or trauma induced Major Depressive Disorder (MDD) and symptoms of depression, as determined by meeting the DSM criteria for PTSD or MDD as a primary diagnosis and scoring ≥10 on the PHQ-9, will be recruited for this study. They will be otherwise healthy adults, aged 18-60, with PTSD or trauma induced MDD as primary diagnosis and without current diagnoses of significant, problematic substance use disorders or with present or past diagnoses of psychosis or bipolar illness. All subjects will receive active TMS, so there is no placebo or sham condition. However, the patients will be blinded as to whether their site of stimulation is based on the clinical standardized targeting method or our novel fMRI-guided targeting method. TMS is administered to one of these two sites over a two-week period, and then TMS will be administered to the other site over a subsequent two-week period following a three week wash out period. All subjects will receive TMS to both sites as a part of the study, but the order is randomized and counterbalanced. All participants will be recruited through the community via study advertisements and through the University of Pennsylvania and the VA. Subjects can express interest by contacting the study staff; in most cases, this will serve as the primary method for acquiring contact information. Physician referrals and the use of the Penn Data Analytics Center will also be incorporated as recruitment methods. Section 4.3 further elucidates all recruitment methods. Prior to any study visits, all subjects will be screened in a telephone interview with a trained member of the study staff or via a self-report screening survey. The first study session will consist of a consenting and extended screening visit. The information collected in this initial visit will determine if the subject meets all inclusion criteria. We will also demonstrate TMS to ensure the subject is comfortable with all study procedures. At the second study session, participants will undergo an MRI procedure for 60 minutes. This will be used to generate the TMS targets for the study. Subjects will then return every weekday (5 days per week, minimum of 4 days per week) over two weeks to receive the TMS treatment (10 sessions). These visits will last approximately 60 minutes each. The daily administration of TMS is a necessary component of the study, as it is consistent with the standard operating procedure for FDAapproved clinical TMS. During the 2 weeks of TMS treatment, subjects will undergo the many of the same clinical assessments used during the screening and baseline visits, in order to examine changes in symptoms. Subjects will then spend 3 weeks away from the study team; during the break, there will be two phone/survey visits used as a safety assessment. After this break, subjects will then return every weekday (5 days per week, minimum of 4 days per week) over two weeks to receive the TMS treatment (10 sessions) to the other site examined in the study. Upon completion of the study, scheduled phone and survey visits will take place every 4 weeks (+/-7 days) over the subsequent 6-month period to monitor continued stability of clinical improvement and/or remaining clinical symptoms. Overall, this study consists of 1 consent/screening visit, 1 MRI scan, 20 total visits for TMS treatment, and 8 phone visits.

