3.2.3 Primary Safety Endpoints

Study follow-up will be conducted monthly, over a 6-month period upon completion of the study in order to determine the duration and stability of clinical improvements. In addition, a clinical assessment will be conducted at the end of each 2-week administration of TMS to any changes in mood and/or symptoms across the study as it is completed.

4 Study Population and Duration of Participation

We plan to enroll 80 patients to obtain useable data from 40 patients diagnosed with PTSD or trauma induced MDD and symptoms of depression, as determined by meeting the DSM criteria for PTSD or trauma induced MDD and having a PHQ-9 score \geq 10, will be recruited for this study. Participants will be otherwise healthy, aged 18-60, without significant concomitant diagnoses.

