additional clinical and neurocognitive assessments and will last approximately 2 hours During these neurocognitive assessments, we may collect EEG and eyetracking data, as in the Baseline Visit.

We may use Neuroflow software for recording participants' heart rate during each TMS treatment session. NeuroFlow's software platform analyzes data from a commercially available, third-heart rate monitor. NeuroFlow follows strict HIPAA guidelines with respect to patient privacy and data security, both from a technical and administrative respective. Only de-identified data will be recorded using this platform, no identifiers will be entered on the platform.

Participants will have a 3 week break from TMS treatment between the first set of TMS sessions (i.e., Visit 2-11/Weeks 1 & 2) and the second set of TBS sessions (i.e., Visits 13-23/Weeks 6 & 7). During this time, participants will not be coming into the lab. However, participants will be scheduled for two phone/survey visits approximately one week, and two weeks (+/- 3 days) following Visit #11, in which clinical assessments will be completed.

Due to the nature of TMS treatment, daily visits are necessary. In the event a participant misses a session, the participant may complete two TMS treatment sessions on one day with ample time in between. In this case, the principal investigator will consider the timeline of missed sessions and evaluate how the missed sessions may be made up appropriately. If too many sessions are missed (as per PI discretion), the participant may be withdrawn from the study without their consent.

6.2.3 3 week break & Phone Calls

Participants will have a 3 week break from TMS treatment between the first set of TBS sessions (i.e., Visit 2-11/Weeks 1 & 2) and the second set of TBS sessions (i.e., Visits 13-22/Weeks 6 & 7). During this time, participants will not be coming into the lab. However, participants will be scheduled for two phone calls and Check-In surveys approximately one week (+/- 3 days) and two weeks (+/- 3 days) following Visit #11, in which clinical assessments will be completed.

6.2.4 Visits 13 - 22

Visits 13-22 are the second set of TMS treatment visits and will consist of identical procedures and will take the same amount of time as Visits 2-11, but stimulations occurring at the targeted site not used in the initial round of TMS treatments Please see sections 6.2.2 for further explanation on these visits.

6.2.5 6 Month Follow-Up: Phone Calls

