6.5 Other Evaluations, Measures

During the course of the study, patients' symptoms will be evaluated in order to determine changes in symptoms across the study. Symptom scales are detailed below in the "Efficacy Evaluations" section.

6.6 *Efficacy Evaluations*

The following clinical assessments will be utilized at baseline, after the first 2-week period of TMS treatment, during the TMS treatment 3 week break, and after the second 2-week period of TMS treatment (the end of the study) to evaluate the efficacy of the TMS interventions in improving clinical symptoms:

- Patient Health Questionnaire (PHQ-9)
- PTSD Checklist for DSM-5 (PCL-5)
- Montgomery-Asberg Depression Scale (MADRS)
- Columbia Suicide Severity Rating Scale (CSSRS)
- Positive and Negative Affect Schedules (PANAS 20 item)
- World Health Organization Quality of Life (WHOQOL-BREF)
- Snaith-Hamilton Pleasure Scale (SHAPS)

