7.4 Statistical Methods

The primary analysis will be a Site x Time ANOVA on the Hamilton Depression rating scale comparing pretreatment to symptoms immediately following each round of stimulation. This test will be augmented by a Site x Time ANOVA for pre-treatment compared with the 6 month timepoint to explore the degree of maintenance of treatment benefits.

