7.4.2 Efficacy Analysis

Efficacy analyses will focus on comparisons between clinical symptoms at baseline, after the first 2-week treatment period, and at the end of the second 2-week treatment period. As noted above, the primary endpoint of this study will be a comparison focusing on clinical improvement due to TMS performed at either the standard brain target or the fMRI-guided brain target.

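### Section 7.4 measures both rounds of the crossover against one pretreatment score, so round-1 benefit that outlasts the 3-week break is credited to the second site and shrinks the site difference

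*Combined protocol and SAP*

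**What the plan says.** Section 3.1 describes a two-site crossover: all patients receive both targets, order is randomised and counterbalanced, and the second site is treated "over a subsequent two-week period following a three week wash out period".

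Section 7.4 sets the primary analysis as a Site x Time ANOVA on the Hamilton scale, "comparing pretreatment to symptoms immediately following each round of stimulation". Section 7.4.2 confines the efficacy analyses to "comparisons between clinical symptoms at baseline, after the first 2-week treatment period, and at the end of the second 2-week treatment period". Neither section mentions period, sequence, carry-over, a separate baseline for round 2, or an analysis of round 1 alone.

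Scores between the rounds are planned. Section 6.6 lists the efficacy scales at baseline, after round 1, and "during the TMS treatment 3 week break, and after the second 2-week period of TMS treatment". Section 6.2.3 schedules the break contacts at "approximately one week (+/- 3 days) and two weeks (+/- 3 days) following Visit #11". Section 3.1 describes the same contacts as a safety assessment. Section 6.2.2 adds a short clinical assessment before and after each stimulation session, with unspecified content, and section 6.2.4 gives round 2 the same procedures.

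On persistence, section 3.2.3 provides monthly follow-up for six months "in order to determine the duration and stability of clinical improvements", and section 7.4 adds an exploratory six-month comparison.

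**The concern.** In a crossover, the score after round 2 reflects the second site's effect plus whatever remains of the first site's effect. Measured from the original pretreatment score, that remainder is counted as benefit of the second site. If the fMRI-guided site is better, as hypothesised, and the same fraction persists at both sites, it leaves the larger remainder, and that remainder goes to the standard site. The error therefore works against the trial's own hypothesis.

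Balancing the orders does not remove this when the remainder depends on which site came first. A period term removes only a shift common to both orders. At stake is the primary objective in section 2.1. If no site difference is found, the planned analysis cannot tell two equal sites from a real difference diluted by carry-over.

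**Working it through.** **Plan's own figure.** The plan gives no figure for the site comparison or for carry-over. Its only sample-size figure is the 6 patients in section 7.3, from g = 1.225, power 0.80 and p 0.05. The one-sample formula reproduces it: n = ((1.960 + 0.842)/1.225)² = 5.2, rounded up to 6. That figure concerns change within patients and says nothing about the difference between sites.

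**Which baseline applies.** Section 7.4 speaks of pretreatment without saying whether each round has its own. Section 7.4.2 lists only one score before any stimulation, so the natural reading is a single original baseline.

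**Timing.** The second break contact falls about 14 days (±3) into a 21-day break, so about 7 days (4 to 10) before round 2. No full section 6.6 assessment is specified at the start of round 2.

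**Expected contrast.** Let a and b be the improvements from the guided and standard sites. Let L be the fraction of round-1 benefit still present after round 2, the same for both sites. Effects are additive and orders balanced. All of these are assumptions; the documents give no value for L.

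- Guided first: improvement a after round 1 and b + La after round 2. Guided minus standard = a - b - La.
- Standard first: b after round 1 and a + Lb after round 2. Guided minus standard = a - b + Lb.
- Average over orders: (a - b) - L(a - b)/2 = (a - b)(1 - L/2).

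The table uses illustrative values a = 8 and b = 6 (true difference 2.0). Power is for a paired t-test with the 40 evaluable patients of section 4.5 and a standardised paired difference of 0.454, which gives 80% power without carry-over.

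| L | Share of true difference | Example estimate | Power |
|---|---|---|---|
| 0 | 100% | 2.00 | 80% |
| 0.25 | 87.5% | 1.75 | 69% |
| 0.5 | 75% | 1.50 | 56% |
| 0.75 | 62.5% | 1.25 | 42% |
| 1 | 50% | 1.00 | 29% |

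**Simulation** (4,000 runs per setting, unit SD, within-patient correlation 0.5, 20 patients per order, true difference 0.45 SD; all assumed).

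- Planned contrast: mean estimate 0.34 at L = 0.5 and 0.22 at L = 1.
- Power of the planned contrast: 46% and 8% with order left out of the model, 55% and 28% with order modelled. Modelling order recovers some power but does not undo the shrinkage.
- Change from a score taken just before round 2, with a stable remainder: estimate 0.45 at every L, but power only about 51%, because two more noisy scores enter.

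**No true difference.** With equal sites and 20 patients per order, the estimate is centred on zero and rejection does not exceed the nominal level (5.0%, 2.2% and 0.3% at L = 0, 0.5 and 1 with order unmodelled). If a share p receives the guided site first and order is not modelled, the expected difference is La(1 - 2p). At 24/16, p = 0.6. With a = 1.225 SD this is 0.5 × 1.225 × (-0.2) = -0.12 SD at L = 0.5 and -0.24 SD at L = 1, favouring the site more often given second. Simulated rejection rates were 6.2% and 5.6%, so the estimate shifts more than the error rate does.

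**Limits of the alternatives.** Round 1 alone, 20 against 20, is free of carry-over but has 80% power only for d of about 0.91. If the remainder falls from L0 before round 2 to L1 after it, the change from the pre-round-2 score estimates (a - b)(1 + (L0 - L1)/2). For 0.5 falling to 0.25 this is 112.5% of the truth.

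**The case against.** The best defence has four parts.

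- **Scores between rounds exist.** A reader of sections 7.4 and 7.4.2 might infer that nothing is measured before round 2 and that carry-over could not be detected. The documents contradict this. Section 6.6 lists the scales during the break expressly to evaluate efficacy. Sections 3.1, 6.2.2 and 6.2.4 also leave open that some scales are taken before round-2 sessions. What stands is that sections 7.4 and 7.4.2 do not use these scores and that no full set is specified at the start of round 2.
- **Durability is studied, not assumed.** A reader might infer from the six-month follow-up that the sponsor expects benefit to last for months. The text sets out to determine, monitor and explore it. But a plan that leaves persistence to six months open gives no ground for assuming complete loss at three weeks.
- **Balanced order protects against a false finding.** This is right under the common-L assumption: the planned contrast shrinks a real difference and does not create one. Carry-over of equal size at both sites also cancels. The protection weakens if order groups become unequal. Section 4.5 expects 40 evaluable patients from 80 enrolled, and section 7.4.1 allows randomisation to be suspended for re-balancing.
- **The remedies cost precision.** This also stands, and it is why neither the pre-round-2 baseline nor the round-1 comparison should automatically replace the crossover estimate.

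A reader might also infer that the comparison is biased whichever baseline is used. Taking the post-round-1 score as the round-2 baseline would give (a - b)(1 + (1 - L)/2), which is 137.5%, 125% and 100% of the truth for L = 0.25, 0.5 and 1. No section specifies that baseline, so this cannot be charged to the plan. The original baseline is itself unbiased at L = 0.

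**Conclusion.** The concern holds as a weakness in the primary analysis. As written, the site contrast is expected to recover 1 - L/2 of the true difference: 87.5%, 75% and 50% for L = 0.25, 0.5 and 1. A difference detectable with 80% power at n = 40 would then have 69%, 56% and 29% power. This rests on additive effects, balanced orders and one L for both sites. L is unknown from the documents, and L = 0 would remove the problem. If persistence differed between sites the formula would change, and the documents give no basis for a figure.

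The consequence is lost power and a null result that is hard to interpret. The documents do not support the stronger conclusion that the design by itself produces a false site difference. Under these assumptions, that needs unequal order groups and an analysis that ignores order. The main reason to act early is that a score not taken immediately before round 2 cannot be recovered later.

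**What to change.** 1. **Sections 6.6 and 7.4.2:** at the first round-2 visit, before any stimulation, collect the scale used in the primary analysis. Section 7.4 names the Hamilton scale, which is not in the section 6.6 list, so reconcile the two first. That visit is numbered 14 in section 3 and 13 in section 6.2.4; use one number.
2. **Section 7.4:** add period and sequence to the model. This guards against a false difference from unequal orders and recovers some power. It does not remove the shrinkage.
3. **Section 7.4:** pre-specify two supporting analyses beside the primary crossover estimate. One is the round-1 comparison between orders, described as free of carry-over but imprecise. The other is change from the pre-round-2 score, described as less precise and as overstating the difference if the remainder decays during round 2. Do not require the estimates to agree before superiority is claimed: with about 20 patients per order, chance disagreement could block a true result.
4. **Section 7.4.2:** use the break scores and the pre-round-2 score to report how much round-1 benefit remains, by first site.

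The cost is one set of scales at a visit already attended in person, plus extra analysis and its wording. The treatment schedule need not change.

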4.5 Total Number of Subjects and Sites

It is expected that approximately 80 subjects will be consented/enrolled at Penn in order to produce 40 evaluable subjects in total (due to missing data, drop out, etc.).

4.6 Vulnerable Populations:

No children, pregnant women, fetuses, neonates, or prisoners are included in this research study.

5 Study Intervention (Study drug, device, biologic, vaccine, food etc.)

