Upon completion of the study, scheduled phone and survey visits will take place every 4 weeks (+/- 7 days) over the subsequent 6-month period to monitor continued stability of clinical improvement and/or remaining clinical symptoms. Each phone and survey visit will include clinical assessments and will take approximately 30-60 minutes.

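### The exploratory 6-month Site x Time ANOVA does not identify a site effect at 6 months unless the round-1 effect is assumed to be fully gone, because every 6-month score follows treatment at both sites

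*Combined protocol and SAP*

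**What the plan says.** Section 7.4 sets the primary analysis as a Site by Time ANOVA from pre-treatment to the end of each round. It then adds "a Site x Time ANOVA for pre-treatment compared with the 6 month timepoint", with the aim of exploring how far benefit is maintained. It does not define Site for this second model, and it does not say whether pre-treatment means the study baseline or the score before each round.

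The design around that model is as follows.

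- Section 3.1: "All subjects will receive TMS to both sites as a part of the study, but the order is randomized and counterbalanced". After the first two-week round, "TMS will be administered to the other site over a subsequent two-week period following a three week wash out period".
- Section 6.2.4: round 2 repeats the round-1 procedures, with "stimulations occurring at the targeted site not used in the initial round of TMS treatments".
- Section 6.2.3: during the break there are two contacts, about one and two weeks after Visit 11.
- Section 6.2.5: "Upon completion of the study, scheduled phone and survey visits will take place every 4 weeks". Section 3.2.3 places this follow-up "over a 6-month period upon completion of the study in order to determine the duration and stability of clinical improvements".
- Section 4.5: recruitment is planned "in order to produce 40 evaluable subjects in total".

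**The concern.** A Site x Time term is normally read as a comparison of sites. At 6 months no participant has a score that follows one site alone: the rounds are three weeks apart and the monthly follow-up begins after both. The model therefore names a factor that its 6-month data do not carry.

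At stake is how the result is labelled. The trial's hypothesis is that the fMRI-guided target is superior, and Section 1.1 presents the monthly follow-up as part of judging how well each site works. A 6-month Site term could easily be reported as site-specific durability, and a value near zero as evidence that the two sites last equally well. The design supports neither statement without a further assumption.

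**Working it through.** **The plan's own figure.** The documents give no figure for the 6-month analysis. The one sample-size figure, 6 patients in Section 7.3, reproduces as a within-patient change by the normal approximation: ((1.960 + 0.842) / 1.225)^2 = 5.23, rounded up to 6. It concerns change over time, not a site contrast, and does not bear on this point.

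**Estimability.** Take 40 evaluable participants (Section 4.5), 20 per order (40 / 2 counterbalanced orders), with scores at baseline and 6 months.

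- Participant and time terms give a model of rank 41.
- Adding a contrast for site received leaves the rank at 41, because the contrast is 0 in every row.
- Adding an order contrast raises the rank to 42.
- With baseline, end of round 1 and end of round 2, adding the most recently treated site raises the rank from 42 to 43. The problem is confined to the 6-month model.

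**What each coding of Site gives.** Let A and B be the changes produced by the guided and standard sites, and assume that the effects of the two rounds add.

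*Coding 1: within participant, shared baseline Y0.* (Y6m - Y0) - (Y6m - Y0) = 0, always.

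*Coding 2: within participant, each round's own pre-treatment score.* (Y6m - preA) - (Y6m - preB) = preB - preA, so the 6-month score drops out. Let rho be the share of the round-1 effect left just before round 2. Guided-first participants give rho*A + period, and standard-first participants give -(rho*B + period). The mean over balanced orders is rho*(A - B)/2. With A = -8 and B = -5 points (assumed, for scale only):

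- rho = 0: 0
- rho = 0.3: 0.3 x (-3) / 2 = -0.45
- rho = 0.6: -0.90
- rho = 1: -1.50

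These values hold whatever happens at 6 months. The contrast depends on the sites, but it is carryover into round 2.

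*Coding 3: between participants, by last site treated* (coding by first site only reverses the sign). Let p1 and p2 be the shares of the round-1 and round-2 effects left at 6 months, equal for both sites. Guided-last participants retain p1*B + p2*A, and standard-last participants retain p1*A + p2*B. The difference is (p2 - p1)*(A - B). The site difference remaining from the last round is p2*(A - B). With A and B unequal, the two agree only if p1 = 0. With the same assumed A - B = -3:

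| p1 | p2 | Contrast (p2 - p1)(-3) | Difference remaining p2(-3) |
|---|---|---|---|
| 0 | 0.6 | -1.8 | -1.8 |
| 0.3 | 0.6 | -0.9 | -1.8 |
| 0.6 | 0.6 | 0 | -1.8 |
| 0.6 | 0.3 | +0.9 | -0.9 |

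**Timing.** Section 6.2.3 puts round 1 in weeks 1-2 and round 2 in weeks 6-7. The sixth 4-weekly contact is 6 x 4 = 24 weeks after round 2, at about week 7 + 24 = 31. Round 1 ended 31 - 2 = 29 weeks before that contact. The ages of the two rounds, 29 and 24 weeks, are close enough that p1 near p2 is plausible, and this is where coding 3 loses a real difference.

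**Precision under coding 3, for scale.** With 20 per order and a two-sided 0.05 t test, an assumed order difference of 0.5 SD has power 0.34. Power reaches 80% at about 0.91 SD.

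**The case against.** The strongest reply concerns coding 3. Section 3.1 calls the break a wash-out. If the round-1 effect is gone, then p1 = 0 and the order contrast is the site difference remaining at 6 months. Round 2 need not have kept its full effect, because the target is what remains and not the acute effect. If both rounds have faded, zero is the correct answer. The shared-retention formula also excludes durability that differs by site, yet with no round-1 effect left the contrast still gives the 6-month site difference. All of this stands.

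It limits what can be claimed. A reader might infer that no coding could ever recover a site effect, that the order contrast is bound to be zero, or that its power cannot exceed 0.34. The documents support none of these. The first fails when p1 = 0. The second fails whenever p1 and p2 differ. The third holds only for an assumed 0.5 SD difference, and the documents give no between-site effect size.

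The reply does not remove the problem. Section 7.4 neither codes Site as order nor states the reliance on wash-out. To read a non-zero contrast as a site effect, round 1 must have left nothing while round 2, with identical procedures and ending only five weeks later, still has an effect. The plan offers no check of that.

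It is also fair to say that the analysis is exploratory, that its stated purpose is maintenance, and that Section 7.4 promises no site-specific 6-month claim. The harm therefore depends on how the Site term is reported.

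**Conclusion.** The concern holds, as a minor point. As written, the 6-month model does not identify a site effect without a strong, untested assumption. Its Site x Time term is zero by construction, carryover before round 2, or treatment order, depending on a coding that the plan leaves open. The first two results follow from algebra and the visit schedule. The third reads as the remaining site difference only if the round-1 effect is fully gone at 6 months (given equal retention at both sites and additive effects). With similar retention it approaches zero even when the sites differ, so a null result would not show equal durability.

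The point values, retention shares and 0.5 SD are illustrations, not estimates from the documents. The stated aim of exploring maintenance can still be met by the pooled change from baseline to 6 months. A reader might infer that the crossover as a whole is compromised. This defect does not reach the primary comparison after each round, where a site term remains estimable.

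**What to change.** In Section 7.4, change the 6-month model as follows.

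- Replace Site with Order (guided first or standard first), and name the study baseline as the pre-treatment score.
- Report the pooled Time effect as durability of the combined two-round course.
- Report Order x Time as an order effect, readable as a site effect only under the stated assumption that no round-1 effect remains at 6 months.
- Make no site-specific durability claim at 6 months, and do not read a null Order x Time term as equal durability.
- Describe short-term site-specific maintenance from the two contacts about one and two weeks after round 1, which precede the crossover.

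The cost is a wording change, with no new visits, data or participants. What is given up is a site-specific durability claim at 6 months, which this design supports only under the assumption above.
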